**NOTE TO THE PROGRAMMER: Table is continued to Week 48 as long as data is available.**

PROTOCOL: INCB 18424-258  
DRUG/INDICATION: Ruxolitinib/Myelofibrosis

(Page 1 of 1)  
VERSION: Final

Table 14.3.2.1

Overall Summary of Treatment-Emergent Adverse Events by Dose Ever Received  
(Population: Safety Evaluable Subjects)

Variable	All Subjects (N=23)	Dose Level (mg) Subjects Ever Received				
		<=5 (N=2)	>5 10 (N=23)	>10 15 (N=14)	>15 20 (N=7)	>20 25 (N=1)
Treatment-Emergent Adverse Events (TEAE) Reported	33	1	8	21	3	0 ( 0.0)
Subjects with a TEAE	10 ( 43.5)	1 ( 50.0)	3 ( 13.0)	5 ( 35.7)	1 ( 14.3)	0 ( 0.0)
Subjects with a Treatment-Related TEAE	2 ( 8.7)	0 ( 0.0)	1 ( 4.3)	1 ( 7.1)	0 ( 0.0)	0 ( 0.0)
Subjects with a Serious TEAE	2 ( 8.7)	1 ( 50.0)	0 ( 0.0)	1 ( 7.1)	0 ( 0.0)	0 ( 0.0)
Subjects with TEAE of Grade 3 or Higher	4 ( 17.4)	1 ( 50.0)	1 ( 4.3)	2 ( 14.3)	0 ( 0.0)	0 ( 0.0)
Subjects with a Dose Increase Due to TEAE	0 ( 0.0)	0 ( 0.0)	0 ( 0.0)	0 ( 0.0)	0 ( 0.0)	0 ( 0.0)
Subjects with a Dose Reduction Due to TEAE	1 ( 4.3)	0 ( 0.0)	0 ( 0.0)	1 ( 7.1)	0 ( 0.0)	0 ( 0.0)
Subjects with Procedures Performed Due to TEAE	2 ( 8.7)	0 ( 0.0)	0 ( 0.0)	2 ( 14.3)	0 ( 0.0)	0 ( 0.0)
Subjects with a TEAE requiring Concomitant Medication	5 ( 21.7)	0 ( 0.0)	1 ( 4.3)	4 ( 28.6)	0 ( 0.0)	0 ( 0.0)
Subjects with Study Drug Withdrawn Due to TEAE	0 ( 0.0)	0 ( 0.0)	0 ( 0.0)	0 ( 0.0)	0 ( 0.0)	0 ( 0.0)
Subjects with an TEAE Leading to Discontinuation from the Study	0 ( 0.0)	0 ( 0.0)	0 ( 0.0)	0 ( 0.0)	0 ( 0.0)	0 ( 0.0)
Subjects with a TEAE Leading to Death	0 ( 0.0)	0 ( 0.0)	0 ( 0.0)	0 ( 0.0)	0 ( 0.0)	0 ( 0.0)

PROGRAM\OUTPUT: T\_AESUM1.SAS\T\_AE1.LST

DATE(TIME): 12DEC11(11:30)

Note 1:TEAEs: AEs that began or worsened from baseline following the first administration of the study drug.

Note 2:Treatment-Related AEs:TEAEs with a possible, probable, definite, or missing causality.

Note 3:Severity vs CTCAE Grade: Mild=Grade 1, Moderate=Grade 2, Severe=Grade 3, Life-Threatening=Grade 4.

Note 4:For an AE that occurred for more than once to a subject, it is counted in the lowest dose when the highest severity grade is recorded.

Reference: Listings 16.2.7.2.1

NOTE to the reviewer: numbers in the shell is from draft DMC output and is intended to show shell only.

PROTOCOL: INCB 18424-258  
DRUG/INDICATION: Ruxolitinib/Myelofibrosis

(Page 1 of 1)  
VERSION: First DMC-Draft

Table 14.3.2.2.1

Summary of Subjects Reporting Treatment-Emergent Adverse Events (All Causalities) by  
MedDRA System Organ Class, Preferred Term, and Maximum Severity  
(Population: Safety Evaluable Subjects)

NOTE TO THE PROGRAMMER: shell will following the standard output.

- Reference: 16.2.7.2.1

PROTOCOL: INCB 18424-258  
 DRUG/INDICATION: Ruxolitinib/Myelofibrosis

(Page 1 of 1)  
 VERSION: First DMC-Draft

Table 14.3.2.2.2

Summary of Subjects Reporting Treatment-Emergent Adverse Events (All Causalities) by  
 MedDRA System Organ Class, Preferred Term, and Dose Level Ever Received  
 (Population: Safety Evaluable Subjects)

Variable	All Subjects (N=23)	CTCAE Grade				
		0 (N=2)	>5 10 (N=23)	>10 15 (N=14)	>15 20 (N=7)	>20 25 (N=1)
Number (%) of Subjects With Any TEAEs	10 ( 43.5)	1 ( 50.0)	3 ( 13.0)	5 ( 35.7)	1 ( 14.3)	0 ( 0.0)
Blood and lymphatic system disorders	1 ( 4.3)	0 ( 0.0)	0 ( 0.0)	1 ( 7.1)	0 ( 0.0)	0 ( 0.0)
Anaemia	1 ( 4.3)	0 ( 0.0)	0 ( 0.0)	1 ( 7.1)	0 ( 0.0)	0 ( 0.0)
Gastrointestinal disorders	6 ( 26.1)	0 ( 0.0)	0 ( 0.0)	4 ( 28.6)	2 ( 28.6)	0 ( 0.0)
Abdominal pain	2 ( 8.7)	0 ( 0.0)	1 ( 4.3)	1 ( 7.1)	0 ( 0.0)	0 ( 0.0)
Anorectal discomfort	1 ( 4.3)	0 ( 0.0)	0 ( 0.0)	1 ( 7.1)	0 ( 0.0)	0 ( 0.0)
Diarrhoea	3 ( 13.0)	0 ( 0.0)	0 ( 0.0)	2 ( 14.3)	1 ( 14.3)	0 ( 0.0)
Dry mouth	1 ( 4.3)	0 ( 0.0)	0 ( 0.0)	0 ( 0.0)	1 ( 14.3)	0 ( 0.0)
Haemorrhoidal haemorrhage	1 ( 4.3)	0 ( 0.0)	0 ( 0.0)	1 ( 7.1)	0 ( 0.0)	0 ( 0.0)
Nausea	1 ( 4.3)	0 ( 0.0)	0 ( 0.0)	1 ( 7.1)	0 ( 0.0)	0 ( 0.0)
. . . . .						
PROGRAM\OUTPUT: T_AESUM1.SAS\T_AE2.LST		DATE (TIME): 12DEC11(11:30)				

Note 1:TEAEs: AEs that began or worsened from baseline following the first administration of the study drug.  
 Note 2:N=the number of subjects who ever took a dose within the dose group, based on which the percent is calculated.  
 Note 3:For an AE that occurred for more than once to a subject, it is counted in the lowest dose when  
 the highest severity grade is recorded.  
 Reference: Listings 16.2.7.2.1

NOTE to the reviewer: numbers in the shell is from draft DMC output and is intended to show shell only.

PROTOCOL: INCB 18424-258  
DRUG/INDICATION: Ruxolitinib/Myelofibrosis

(Page 1 of 1)  
VERSION: First DMC-Draft

Table 14.3.2.3.1

Summary of Subjects Reporting Treatment-Emergent Adverse Events (All Causalities) by  
MedDRA Preferred Term (Sorted by Decreasing Frequency) and Maximal Severity  
(Population: Safety Evaluable Subjects)

NOTE TO THE PROGRAMMER: shell will following the standard output.

- Reference: 16.2.7.2.1

PROTOCOL: INCB 18424-258  
DRUG/INDICATION: Ruxolitinib/Myelofibrosis

(Page 1 of 1)  
VERSION: First DMC-Draft

Table 14.3.2.3.2

Summary of Subjects Reporting Treatment-Emergent Adverse Events (All Causalities) by  
MedDRA Preferred Term (Sorted by Decreasing Frequency) and Dose Ever Received  
(Population: Safety Evaluable Subjects)

NOTE TO THE PROGRAMMER: shell will following the standard output and table will be similarly programmed as 14.3.2.2.2.

- Reference: 16.2.7.2.1

NOTE: Shells for the following tables are not provided here but they will be programmed similarly to those presented above.

14.3.2.3.2	Summary of Subjects Reporting Treatment-Emergent Adverse Events (All Causalities) by MedDRA Preferred Term (Sorted by Decreasing Frequency) and Dose Level Ever Received	Safety
14.3.2.3.3	Summary of Subjects Reporting Treatment-Emergent Hemorrhage Adverse Events (All Causalities) by MedDRA Preferred Term and Dose Level Ever Received	Safety
14.3.2.3.4	Summary of Subjects Reporting Treatment-Emergent Hemorrhage Adverse Events (All Causalities) of Grade 3 or Higher by MedDRA Preferred Term and Dose Level Ever Received	Safety
14.3.2.4.1	Summary of Subjects Reporting Treatment-Emergent Treatment-Related Adverse Events (All Causalities) by MedDRA System Organ Class, Preferred Term, and Maximum Severity	Safety
14.3.2.4.2	Summary of Subjects Reporting Treatment-Emergent Treatment-Related Adverse Events (All Causalities) by MedDRA System Organ Class, Preferred Term, and Dose Level Ever Received	Safety
14.3.2.5.1	Summary of Subjects Reporting Treatment-Emergent Serious Adverse Events (All Causalities) by MedDRA System Organ Class, Preferred Term, and Dose Level Ever Received	Safety
14.3.2.6	Summary of Subjects Reporting Treatment-Emergent Adverse Events (All Causalities) Leading to Study Medication Decrease or Interruption by MedDRA System Organ Class, Preferred Term, and Dose Level Ever Received	Safety
14.3.2.7	Summary of Subjects Reporting Treatment-Emergent Adverse Events (All Causalities) Leading to Study Discontinuation by MedDRA System Organ Class, Preferred Term, and Dose Level Ever Received	Safety
14.3.2.8	Summary of Subjects Reporting Treatment-Emergent Adverse Events (All Causalities) Leading to On-Study Death by MedDRA System Organ Class, Preferred Term, and Dose Level Ever Received	Safety

NOTE: the following lab tables will be programmed according to standard output.

14.3.3.1.1	Summary of Laboratory Values – Hematology	Safety
14.3.3.1.2	Shift Summary of Laboratory Values in Normal Ranges - Hematology	Safety
14.3.3.2.1	Summary of Laboratory Values – Serum Chemistry	Safety
14.3.3.2.2	Shift Summary of Laboratory Values in Normal Ranges – Serum Chemistry	Safety
14.3.3.3.1	Summary of Laboratory Values – Coagulation	Safety
14.3.3.3.2	Shift Summary of Laboratory Values in Normal Ranges – Coagulation	Safety
14.3.3.4.1	Summary of Laboratory Values – Urinalysis	Safety
14.3.3.4.2	Shift Summary of Laboratory Values in Normal Ranges – Urinalysis	Safety
14.3.3.5.1	Shift Summary of Laboratory Values in CTC Grade - To the Worst Abnormal Value (Tests with One Directional CTC Grade)	Safety
14.3.3.5.2	Shift Summary of Laboratory Values in CTC Grade - To the Worst Abnormal Value (Tests with Two Directional CTC Grade)	Safety

PROTOCOL: INCB 18424-258  
 DRUG/INDICATION: Ruxolitinib/Myelofibrosis

(Page 1 of 1)  
 VERSION: Final

Table 14.3.3.6.1

Summary of Subjects with Treatment Emergent Thrombocytopenia of Grade 4 as Derived from Laboratory Data  
 by Last Dose Before Onset  
 (Population: Safety Evaluable Subjects)

MedDRA Preferred Term	All Subjects (N=xx)	Dose Level (mg) Subjects Ever Received					
		<=5	>5 10	>10 15	>15 20	>20 25	>25
		N=xx	N=xx	N=xx	N=xx	N=xx	N=xx
Number (%) of Subjects With Grade 4 Thrombocytopenia [1]	xx ( xx.x)	xx xx%	xx xx%	xx xx%	xx xx%	xx xx%	xx xx%

PROGRAM\OUTPUT: T\_xxxx.SAS\T\_xxxxx.LST

DATE (TIME) : DDMMYY (HH:MM)

Treatment-Emergent AEs: AEs that began or worsened from baseline following the first administration of study drug.

Note: Subjects are counted only once under in the lowest dose group.

Note: N=the number of subjects who ever took a dose within the dose group, based on which the percent is calculated.

Note: AEs that occurred following the date of treatment crossover were not included.

[1] Grade 4 Thrombocytopenia is defined as any occurrence of a treatment emergent hematology lab below 25 GI/L

Reference: Listing 16.2.8.1.4

PROTOCOL: INCB 18424-258  
DRUG/INDICATION: Ruxolitinib/Myelofibrosis

(Page 1 of 1)  
VERSION: Final

Table 14.3.3.6.2

Summary of Subjects with Treatment Emergent Anemia of Grade 4 as Derived from Laboratory Data  
by Last Dose Before Onset  
(Population: Safety Evaluable Subjects)

NOTE TO THE PROGRAMMER: similarly program this as Table 14.3.3.6.1, just need to update footnote about G4 anemia.

NOTE: the following vital sign tables will be programmed according to standard output.

14.3.4.1	Summary of Systolic Blood Pressure	Safety
14.3.4.2	Summary of Diastolic Blood Pressure	Safety
14.3.4.3	Summary of Heart Rate	Safety
14.3.4.4	Summary of Respiratory Rate	Safety
14.3.4.5	Summary of Body Temperature	Safety

NOTE: the following laboratory tables will be programmed according to standard output.

14.2.1.1	Scatter Plot of Percent Change from Baseline in Spleen Volume at Week 24 vs. Final Titrated Dose Level	ITT
14.2.1.2	Scatter Plot of Percent Change from Baseline in Total Symptom Score at Week 24 vs. Final Titrated Dose Level	ITT
14.2.1.3	Scatter Plot of Percent Change from Baseline in Spleen Volume vs. Percent Change in Total Symptom Score at Week 24	ITT
14.2.2.1	Bar Plot of Percent of Subjects with $\geq 35\%$ Reduction from Baseline in Spleen Volume at Week 24 by Final Titrated Dose Group	ITT
14.2.2.2	Bar Plot of Percent of Subjects with $\geq 10\%$ Reduction from Baseline in Spleen Volume at Week 24 by Final Titrated Dose Group	ITT
14.2.2.3.1	Mean (95%) Percent Change from Baseline in Spleen Volume at Week 24	ITT
14.2.2.3.2	Mean (95%) Percent Change from Baseline in Spleen Volume at Week 24 by Final Titrated Dose Group	ITT
14.3.1.1.1	Subject Laboratory Value over Time: Hemoglobin (G/L)	Safety
14.3.1.1.2	Mean (95% CI) Laboratory Value Over Time: Hemoglobin (G/L)	Safety
14.3.1.2.1	Subject Laboratory Value over Time: Platelet (GI/L)	Safety
14.3.1.2.2	Mean (95% CI) Laboratory Value Over Time: Platelet (GI/L)	Safety
14.3.1.3.1	Subject Laboratory Value over Time: WBC (GI/L)	Safety
14.3.1.3.2	Mean (95% CI) Laboratory Value Over Time: WBC (GI/L)	Safety
14.3.1.4.1	Subject Laboratory Value over Time: Neutrophils (GI/L)	Safety
14.3.1.4.2	Mean (95% CI) Laboratory Value Over Time: Neutrophils (GI/L)	Safety

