11. SAFETY MONITORING AND REPORTING

11.1. Adverse Events

11.1.1. Definitions and Reporting

An Adverse Event (AE) for the purposes of this protocol is defined as the appearance of (or worsening of any pre-existing) undesirable sign(s), symptom(s), or medical condition(s) that occur after a subject's signed informed consent has been obtained. Abnormal laboratory values or test results occurring after informed consent constitute AEs only if they induce clinical signs or symptoms, are considered clinically meaningful, require therapy (eg, hematologic abnormality that requires transfusion), or require changes in study drug(s).

Adverse Events that begin or worsen after informed consent should be recorded in the Adverse Events section of the CRF. Conditions that were already present at the time of informed consent should be recorded in the medical history section of the CRF. Adverse Event monitoring should be continued through the follow-up visit or for at least 30 days following the last dose of study treatment, whichever comes later. Adverse Events (including lab abnormalities that constitute AEs) should be described using a diagnosis whenever possible, rather than individual underlying signs and symptoms. When a clear diagnosis cannot be identified, each sign or symptom should be reported as a separate AE.

Adverse Events will be assessed according to the Common Terminology Criteria for Adverse Events (CTCAE) v4.03. If CTCAE grading is not used for a study, the severity of mild, moderate, severe, and life-threatening, or Grades 1 - 4, will be used. CTCAE Grade 5 (death) will not be used in this study; rather, information about deaths will be collected as an outcome of the event. The occurrence of AEs should be sought by non-directive questioning of the subject during the screening process after signing informed consent and at each visit during the study. Adverse Events may also be detected when they are volunteered by the subject during the screening process or between visits, or through physical examination, laboratory test, or other assessments. As far as possible, each AE should be evaluated to determine:

- The severity grade (CTCAE Grade 1-4)
- Reasonable possibility that AE is related to the study treatment: (no, yes)
- Reasonable possibility that AE is related to a study procedure: (no, yes)
- Start and end dates, unless unresolved at final exam

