11.3.2. Reporting

To ensure subject safety, every SAE, regardless of suspected causality, occurring after the subject has signed the informed consent form (ICF) and until (at least) the Follow-up Visit or 30 days after the subject has stopped study treatment (whichever comes later) must be reported to the Sponsor or designee within 24 hours of learning of its occurrence. Any SAEs experienced after this period of at least 30 days should only be reported to the Sponsor, or designee, if the Investigator suspects a causal relationship to the study medication. Recurrent episodes, complications, or progression of the initial SAE must be reported as the follow-up to the original episode within 24 hours of the Investigator receiving the follow-up information. An SAE occurring at a different time interval or otherwise considered completely unrelated to a previously reported one should be reported separately as a new event. Serious AE collection begins after the subject has signed the ICF. If a subject experiences an SAE after signing the ICF, but prior to receiving study medication, the event will **not** be collected unless the Investigator feels the event may have been caused by a protocol procedure. Previously planned (prior to signing the ICF) surgeries should not be reported as SAEs unless the underlying medical condition worsens over the course of the study.

Information about all SAEs is collected and recorded on the Serious Adverse Event Report Form. The Investigator must assess and record the relationship of each SAE to each specific study medication (if there is more than 1), complete the SAE Report Form in English, and send the completed, signed form by fax within 24 hours to the Sponsor (or designee). The investigator must assess if there is a Reasonable possibility that the SAE is related to the study treatment: no (unrelated), yes (related).

SAEs related to unblinded comparator drugs or concomitant medications/drug delivery systems are reported directly to the manufacturers of those drugs/devices in accordance with the package insert.

The telephone and facsimile number of the Sponsor's contact persons, specific to the study, are listed in the investigator folder provided to each site. The original copy of the SAE Report Form and the fax confirmation sheet must be kept with the case report form documentation at the study site.

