12.2. Statistical Analyses

12.2.1. Primary Analyses

Co-Primary Endpoints:

- Correlation of % change in spleen volume at Week 24 compared to baseline versus final titrated dose.
- Correlation of % change in Total Symptom Score as measured by the modified MFSAF v2.0 diary at Week 24 compared to baseline versus final titrated dose.

The null hypothesis is that the correlation between percent change in spleen volume or total symptom score and final titrated dose is zero. The test will be based on the t test for a product-moment correlation coefficient:

$$t = r_{xy} \sqrt{(n - 2) / (1 - r_{xy}^2)}$$

(Cohen 1988, Formula 3.1.1)

A two-sided alpha of 5% will be used. With a sample size of 150, the critical correlation that is needed to reject H_0 is 0.16. If the absolute value of the observed correlation is 0.16 or higher, H_0 will be rejected. In order to keep the overall alpha at 5%, a sequential testing procedure will be used: First we will test the correlation with % change in spleen volume, and only if the null hypothesis of no correlation can be rejected will we continue to test the correlation with % change in Total Symptom Score.

Safety Endpoints:

Safety and tolerability will be assessed by monitoring the frequency, duration and severity of adverse events, performing physical examinations, collecting vital signs, collecting laboratory data for hematology, serum chemistry, coagulation parameters, and lipid panel through Week 156.

Change in platelet count from baseline to each visit where the variables are measured will be tabulated with summary statistics.

Proportion of subjects with new onset of Grade 4 thrombocytopenia events, and proportion of subjects with new onset of Grade 2 or higher hemorrhage, as measured by CTCAE will be tabulated with summary statistics. The hazard functions of time to onset of the above two safety measures will be estimated using life table method.

Adverse events will be tabulated by the Medical Dictionary for Regulatory Activities (MedDRA[®]) preferred term and by system organ class. Severity of AEs will be based on the CTCAE scale as indicated in [Section 11.1.1](#).

The subset of AEs that are considered by the Investigator to be related to study drug will be considered to be treatment-related AEs. If the Investigator does not specify the relationship of the AE to study drug, the AE will be considered to be treatment-related. The incidence of AEs and treatment-related AEs will be tabulated.

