## **5.8. Adverse Events and Missing Data**

A treatment-emergent adverse event (TEAE) is any AE either reported for the first time or worsening of a pre-existing event after first dose of study medication. Analysis of AEs will be limited to TEAEs, but data listings will include all AEs.

Severity of AEs will be described and graded using the National Cancer Institute (NCI) Common Terminology Criteria for Adverse Events (CTCAE). CTCAE v4.03 is used for this protocol. If the toxicity is not included in the CTCAE v4.03 criteria it will be rated on a 1 to 4 scale as follows: mild = 1; moderate = 2; severe = 3; and life-threatening = 4.

An AE will also be assessed by its relationship to study medication as well as by seriousness. These assessments will be directly from data collected on eCRFs and are described in details in the protocol.

Any missing onset date, causality, or severity must be queried for resolution. Unsolved missing values will be handled according to the following rules:

- An unsolved missing causality will be considered treatment related
- An unsolved missing severity will be identified as an unknown severity

- For purposes of analysis, all AEs will be considered TEAEs unless the AE can unequivocally be defined as not treatment emergent. Therefore, an unsolved missing onset date will be considered treatment emergent, with the following examples illustrating exceptions:
  - If the stop/resolution date is before the first dose date on Day 1, then the AE will be considered as not being treatment emergent.
  - If both the month and day are missing, and the last day of the year is before the first dose date on Day 1, then the AE will not be considered treatment emergent.
  - If only the day is missing, and the last day of the month is before the first dose date on Day 1, then the AE will not be considered treatment emergent.
  - If only the day is missing, and the first day of the month is after the first dosing date on Day 1, then the AE will be considered treatment emergent.

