14.3.1.1	Summary of Exposure and Duration of Exposure to Study Medication Through Week 24	Safety
14.3.1.2	Summary of Exposure to Ruxolitinib Through Week 4	Safety
14.3.1.3	Summary of Average Daily Dose of Ruxolitinib by Study Week	Safety
Safety: Adverse Events		
14.3.2.1	Overall Summary of Treatment-Emergent Adverse Events by Dose Level Ever Received	Safety
14.3.2.2.1	Summary of Subjects Reporting Treatment-Emergent Adverse Events (All Causalities) by MedDRA System Organ Class, Preferred Term, and Maximum Severity	Safety

Table Number	Title	Population
14.3.2.2.2	Summary of Subjects Reporting Treatment-Emergent Adverse Events (All Causalities) by MedDRA System Organ Class, Preferred Term, and Dose Level Ever Received	Safety
14.3.2.3.1	Summary of Subjects Reporting Treatment-Emergent Adverse Events (All Causalities) by MedDRA Preferred Term (Sorted by Decreasing Frequency) and Maximal Severity	Safety
14.3.2.3.2	Summary of Subjects Reporting Treatment-Emergent Adverse Events (All Causalities) by MedDRA Preferred Term (Sorted by Decreasing Frequency) and Dose Level Ever Received	Safety
14.3.2.3.3	Summary of Subjects Reporting Treatment-Emergent Hemorrhage Adverse Events (All Causalities) by MedDRA Preferred Term and Dose Level Ever Received	Safety
14.3.2.3.4	Summary of Subjects Reporting Treatment-Emergent Hemorrhage Adverse Events (All Causalities) of Grade 3 or Higher by MedDRA Preferred Term and Dose Level Ever Received	Safety
14.3.2.4.1	Summary of Subjects Reporting Treatment-Emergent Treatment-Related Adverse Events (All Causalities) by MedDRA System Organ Class, Preferred Term, and Maximum Severity	Safety
14.3.2.4.2	Summary of Subjects Reporting Treatment-Emergent Treatment-Related Adverse Events (All Causalities) by MedDRA System Organ Class, Preferred Term, and Dose Level Ever Received	Safety
14.3.2.5.1	Summary of Subjects Reporting Treatment-Emergent Serious Adverse Events (All Causalities) by MedDRA System Organ Class, Preferred Term, and Dose Level Ever Received	Safety
14.3.2.6	Summary of Subjects Reporting Treatment-Emergent Adverse Events (All Causalities) Leading to Study Medication Decrease or Interruption by MedDRA System Organ Class, Preferred Term, and Dose Level Ever Received	Safety
14.3.2.7	Summary of Subjects Reporting Treatment-Emergent Adverse Events (All Causalities) Leading to Study Discontinuation by MedDRA System Organ Class, Preferred Term, and Dose Level Ever Received	Safety

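### Note 2 of the Table 14.3.2.1 shell defines treatment-related events on a possible/probable/definite scale, but the protocol records causality as no or yes; the note should be aligned with protocol 12.2.1 and SAP 5.8

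*SAP*

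**What the plan says.** Recording. Protocol 11.1.1 asks for a two-level answer on each adverse event, under the item "Reasonable possibility that AE is related to the study treatment: (no, yes". Protocol 11.3.2 uses the same two levels for serious events: "no (unrelated), yes (related".

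Analysis rule. Protocol 12.2.1 states: "The subset of AEs that are considered by the Investigator to be related to study drug will be considered to be treatment-related AEs". It then covers the unanswered case: "If the Investigator does not specify the relationship of the AE to study drug, the AE will be considered to be treatment-related". SAP 5.8 agrees. It says of relationship and seriousness: "These assessments will be directly from data collected on eCRFs and are described in details in the protocol". It also treats a causality still missing after query as related.

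Shell. In SAP Appendix B, Note 2 under Table 14.3.2.1 defines treatment-related AEs as "TEAEs with a possible, probable, definite, or missing causality". No other shell shown defines relatedness. Tables 14.3.2.4.1 and 14.3.2.4.2 have no shell of their own; Appendix B says they will be modelled on the shells that precede them. Both titles, in SAP 10.1 and again in Appendix B, contain "Treatment-Emergent Treatment-Related Adverse Events (All Causalities" followed by a closing parenthesis.

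**The concern.** The categories in Note 2 do not match the answers the protocol allows. The answer yes is not on the note's list, so a program that selects records by the note misses exactly the events that protocol 12.2.1 puts first.

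The incidence of treatment-related AEs is a planned tabulation under a primary safety objective. SAP 8.1 lists it in both the high-level summary and the summaries by MedDRA term. Because Note 2 is the only relatedness definition in the shells, an error there could carry into the two treatment-related tables built from them. Even if the program is right, the printed footnote would misdescribe what was counted.

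The titles of those two tables add a smaller ambiguity. They name both the treatment-related set and the all-causality set, which SAP 8.1 treats as different.

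**Working it through.** No sample size, power or alpha figure bears on this point. The check applies each rule to each value the protocol allows.

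**Step 1. The shell's own figure.** The Table 14.3.2.1 shell shows 2 of 23 subjects with a treatment-related TEAE: 2/23 = 8.7%, as printed. The two populated dose columns also check: 1/23 = 4.3% and 1/14 = 7.1%. A note under the shell says that the numbers come from draft data monitoring output and only illustrate the layout.

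**Step 2. The two rules on the recorded values.** Rule A is Note 2 (possible, probable, definite or missing). Rule B is protocol 12.2.1 with SAP 5.8 (yes or missing).

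| Recorded causality | Rule A counts it | Rule B counts it |
|---|---|---|
| yes | no | yes |
| no | no | no |
| missing | yes | yes |

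The rules differ on the yes row and nowhere else. Under Rule A, 0% of yes events count; under Rule B, 100% do.

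**Step 3. Effect on the printed row.** Let M be the share of subjects with at least one missing-causality TEAE. Let R be the share with at least one yes TEAE and none with missing causality. Rule A prints M. Rule B prints R + M. The shortfall is R.

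The documents give neither R nor M for the final data. With M assumed at 1% and R assumed between 20% and 80%:

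- R = 20%: Rule A prints 1%; Rule B prints 20% + 1% = 21%.
- R = 80%: Rule A prints 1%; Rule B prints 80% + 1% = 81%.

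These are bounds on a literal reading, not forecasts.

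**Step 4. Is the graded scale defined anywhere else?** No. Protocol 4.3.1 refers to hemorrhage events assessed as at least possibly related, but that is background on dose interruption and does not set how causality is recorded. SAP 5.8 refers back to the eCRF and the protocol and introduces no scale of its own.

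**Step 5. What does not depend on relatedness.** SAP 8.1 bases new-onset Grade 4 thrombocytopenia on laboratory data, and Grade 2 or higher hemorrhage on the SMQ terms and CTCAE grade. The review thresholds in protocol 11.7.3 and 11.7.4 count events without a relatedness condition, and 11.7.2 requires notification whatever the suspected cause. The all-TEAE, SAE and Grade 3 or 4 summaries do not use causality either.

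**The case against.** The strongest reply is that the governing rule is already right in two places. Protocol 12.2.1 and SAP 5.8 both give a workable definition, and Note 2 is a footnote in an appendix shell. For the row to fail, a programmer would have to follow the footnote, ignore both body rules, and match on codes that a yes/no dataset does not contain. Mapping yes to related is the more likely outcome. This stands, and it limits the point to the written rule.

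Second, the mismatch may be a version effect. The SAP covers protocol Amendment 1 (17 August 2011) and CRF Study Design Version 1.6. The protocol at hand is later: it reports interim results and treatment to Week 156, whereas the SAP describes continuation until commercial availability. The Amendment 1 causality item cannot be seen. This also stands, but it does not remove the need for a change. If the scale was always yes/no, Note 2 is wrong; if it changed, Note 2 omits the current yes and a mapping is missing.

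Third, other shells carry apparent leftover text: a treatment-crossover note under Table 14.3.3.6.1 in a single-arm study, and a CTCAE grade header over the dose columns of Table 14.3.2.2.2. Template carry-over is therefore a plausible explanation for Note 2, though it remains an inference.

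A reader might infer that the treatment-related row will come out close to zero. The documents do not support that: the body rule is correct, and the illustrative row shows 2 of 23. That row does not settle the matter the other way, since it is marked as layout only and could reflect missing causality. A reader might also infer that Tables 14.3.2.4.1 and 14.3.2.4.2 will duplicate the all-TEAE tables. SAP 8.1 lists treatment-related AEs by organ class and preferred term separately from all TEAEs, so the parenthesis in the titles is a wording error and does not show that a different event set was chosen.

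**Conclusion.** The point holds as a conflict between a stated selection rule and the governing definition, and it should be corrected. Read literally on yes/no data, Note 2 omits every event the investigator called related and keeps only those with missing causality, a shortfall equal to R. That size is a worst case. It assumes that causality is held as yes/no, as the protocol at hand says, and that the note is programmed as written over the body text.

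The consequence is confined to the descriptive treatment-related summaries. No hypothesis test, named safety endpoint or data monitoring threshold changes. The all-causalities wording is a minor title correction.

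**What to change.** 1. Replace Note 2 of the Table 14.3.2.1 shell with: *Treatment-related AEs: TEAEs with relationship to study treatment = yes, or missing.*
2. State that the same definition applies to Tables 14.3.2.4.1 and 14.3.2.4.2.
3. Check the causality item on CRF Study Design Version 1.6. If any records were collected on a graded scale, add one sentence giving the mapping to yes/no.
4. Delete the all-causalities parenthesis from the titles of Tables 14.3.2.4.1 and 14.3.2.4.2, in SAP 10.1 and in Appendix B.

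The cost is one footnote, one cross-reference, two titles and, if needed, one mapping sentence. Data collection, clinical conduct and the efficacy analyses do not change.
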